2017-144 Monitoring Telotristat Ethyl Inhibition of Tryptophan hydroxylase (TPH) in Neuroendocrine Tumors Using α -[¹¹C]methyl-L-tryptophan (AMT)-PET Version 1: 11/27/17; Revised 09/10/19; Revised 05/26/20

Table of contents:

	Protocol summary	2
١.	Objectives	3
II.	Background	3
III.	Patient selection	6
IV.	Registration procedures	7
٧.	Treatment plan	8
VI.	Adverse events	8
VII.	Measurement of effect (AMT-PET)	11
VIII.	Statistical plan	12
IX.	Data and safety monitoring	13
Х.	References	15

Principal Investigator: [name], PhD [contact]; [contact] Email: [contact] [name]

Co- Investigator: [name], PhD [name], PhD [name] [name] [name], MSN, CNP [name] - Biostatistician

PROTOCOL SUMMARY

OBJECTIVES:

Primary objective is to show that telotristat ethyl (Xermelo[™]), a recently FDA-approved TPH inhibitor drug, will decrease tumoral AMT uptake and trapping as compared to values measured at baseline before the start of treatment. Secondary objective is to show that neuroendocrine tumors (NETs) will have increased AMT uptake on positron emission tomography (PET), as compared to surrounding non-tumor tissue at baseline.

PATIENT POPULATION:

- 1. Histopathologically confirmed, well-differentiated metastatic NETs.
- Patients receiving stable-dose somatostatin analogs (SSAs, long-acting release [LAR], depot) for > 3 months before enrollment.

STUDY DESIGN:

Imaging will be done with AMT-PET/CT, under separate protocol 2011-053, at baseline and after 9-14 days treatment on telotristat ethyl, 250 mg po three times daily.

EVALUATION:

Prior to PET imaging: Physical exam, CBC and Multiphasic (electrolytes, renal and liver function) drawn within 28 days of start of the study as part of routine care. Radiology testing to measure tumor size (for example, CT scans, MRI scans, PET scans) which are part of routine care. Scan may be done within 8 weeks of the start of the study. A negative urine or blood pregnancy test must be obtained in women with child bearing potential on the day of the first PET scan.

PRIMARY and Secondary ENDPOINTS:

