A venous line will be established for injection of AMT tracer (0.1 mci/kg). All PET images will be corrected for attenuation using the CT scan. After injection a CT scan is performed, immediately followed by a 60-minute dynamic PET scan of the area of interest that includes the tumor. The total dose for the PET/CT scan will be in compliance with guidelines for research studies prescribed by the Code of Federal Regulation.

Quantitative assessment of AMT tumor uptake. The AMT uptake in ROIs representing tumor and non-tumor tissue will be characterized in the following two ways:

1. Standardized uptake values (SUVs): The SUV calculation relates tracer concentration in tissue to the dose injected and the subject's mass (SUV = tissue concentration in ROI /injected dose per weight). First, decay-corrected time-activity curves will be generated to evaluate the tumoral accumulation and washout of the tracer during the scanning period. Since all subjects receive the same injected dose based upon weight (0.1 mCi/kg), the SUV images will be directly obtained by averaging values from frames of the dynamic image sequence during which time there is the most metabolic product. The timing of these frames will be determined after examination of the time-activity curves to identify the optimal time frame when tracer uptake reaches a plateau. The Standard Uptake Value maximum (SUVmax) will measure the most active pixel in the tumor and the two adjacent planes. Change in SUVmax will serve as the primary aim. Regions of Interest (ROIs) for the SUVmean will be drawn using isocontours set at 50% of the SUVmax. Results will be indicated as percent change in the uptake between the two scans.

2. Compartmental modeling (in tumors with the left ventricle of the heart in the field-of-view). In addition to the semi-quantitative SUV analysis, in tumors where the left ventricle of the heart is in the field-of-view, we will also assess the data with tracer kinetic analysis using a 3-compartment model, as described in our previous studies in lung and breast tumors (Juhasz et al., 2009; 2012). This analysis will allow a more detailed analysis of tumoral tracer transport and trapping parameters at baseline and their changes after TPH inhibitor treatment.

3. Primary endpoint and secondary endpoints:

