The proportion of patients who achieved SUVmax reduction of 20% or more between baseline and followup will be the primary measurement. We will also assess if the NET is visible above background at baseline and will also quantify the percent difference in AMT uptake between the tumor mass and background. In addition, using time-activity curves, we will also identify the optimal time frame where tumoral AMT uptake peaks. The change in SUVmean will also be measured.

VIII. STATISTICAL PLAN

Design This is a single arm single institution prospective proof-of-concept study. **Primary endpoint** is the proportion of patients who achieved SUVs reduction of 20% or more. The primary endpoint will be reported as proportions with two-sided exact 95% confidence limit. The other categorical endpoints will be reported as mean and standard deviation. Paired t test will be used for pre- and post- treatment SUVs if normality assumption holds. The relationship of one PET parameter to another will be visualized with scatter plot and measured using linear regression models. Statistical analysis will be performed using R version 3.3.2. **Power calculation:** This is a Proof-of-Concept trial where the goal is to demonstrate the feasibility and to show the proportion of patients who achieved SUVs reduction is at least 0.2 or higher. Hence, we will calculate the minimum sample size to achieve a confidence lower limit no less than 0.2. A sample size of 6 produces a one-sided 90% lower-limit confidence interval at (0.201, 1) using Clopper-Pearson formula when the expected proportion is 0.5. **Study Duration**: The accrual rate is 6/year and minimum follow -up for each patient will be 3 months. The study will require 15-18 months to complete.

IX. DATA AND SAFETY MONITORING/STUDY AUDITS/STUDY ETHICS

Data and Safety Monitoring

- 1. Scheduled meetings will be held monthly or more frequently depending on the activity of the protocol. These meetings will include the protocol investigators and research staff involved with the conduct of the protocol.
- 2. During these meetings the investigators will discuss:
 - Safety of protocol participants (adverse events and reporting)
 - Validity and integrity of the data (data completeness on case report forms and complete source documentation)

- Enrollment rate relative to expectation of target accrual, (eligible and ineligible participants)
- Retention of participants, adherence to the protocol and protocol deviations
- Protocol amendments

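### The SUV frame window is chosen after the curves are seen, with no index-lesion rule and no stated masking to scan order; coding the 12 scans and locking these choices would protect the primary endpoint cheaply

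*Combined protocol and SAP*

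**What the plan says.** The Statistical Plan (Section VIII) describes the design as follows: "This is a single arm single institution prospective proof-of-concept study". The expected direction is declared in the Protocol Summary, where the aim is to show that the drug "will decrease tumoral AMT uptake and trapping as compared to values measured at baseline before the start of treatment". The primary endpoint is a per-patient dichotomy (Section VII, item 3): "The proportion of patients who achieved SUVmax reduction of 20% or more between baseline and followup will be the primary measurement".

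Section VII states how the value is obtained: "The AMT uptake in ROIs representing tumor and non-tumor tissue will be characterized in the following two ways". SUV images are averages over selected frames of the 60-minute dynamic scan, and on the selection the text says "The timing of these frames will be determined after examination of the time-activity curves". The aim is a window in which uptake has levelled off. Two steps are rule-based. For the primary measure, "The Standard Uptake Value maximum (SUVmax) will measure the most active pixel in the tumor and the two adjacent planes". For the secondary one, "Regions of Interest (ROIs) for the SUVmean will be drawn using isocontours set at 50% of the SUVmax".

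Three things are not stated: whether one window applies to both scans of a patient or to all patients; which lesion supplies the primary value when a patient has more than one (Section III asks for at least one lesion over 2 cm on standard imaging); and whether the person doing the quantification is masked to scan order. Coded scans, random reading order and a second or independent reader are not mentioned either.

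**The concern.** The frame window and the lesion are settled before the hottest pixel is read, so they act on the primary value ahead of the rules that make SUVmax reproducible. If they are settled with the curves in view, and by someone who knows which scan is on drug, borderline choices can lean toward the expected fall without any intent.

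Two features of the design make this matter. There is no control arm, so a lean that depends on scan order is not separated from a drug effect within the planned analysis. The endpoint is also a hard cut in 6 patients, so a small shift in one borderline patient changes the count by one.

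**Working it through.** **1. The plan's own figure.** Inputs from Section VIII: n = 6, expected proportion 0.5 (x = 3 responders), one-sided 90% Clopper-Pearson lower limit, target 0.2. The lower limit is the 0.10 quantile of Beta(x, n − x + 1). For x = 3 this is Beta(3, 4), which gives 0.2009. The stated 0.201 is reproduced.

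**2. What one patient is worth.** For x = 2 the limit is the 0.10 quantile of Beta(2, 5), which is 0.093. The goal is therefore met at 3/6 and missed at 2/6. Section VIII also plans to report a two-sided 95% interval. Its lower limit is 0.118 at 3/6 and 0.223 at 4/6, so on that scale too a single patient decides whether 0.2 is cleared.

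**3. Illustration of a lean.** The documents give no test-retest variability for AMT SUVmax and no size for any reading lean, so both are assumptions. Let the log ratio of Scan 2 to Scan 1 be normal with no drug effect. A per-scan CV of about 10 to 20% gives an SD of roughly √2 × CV, or 0.14 to 0.28. A lean multiplies the ratio by (1 − lean). The chance that a patient is counted as a responder is

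p = Φ((ln 0.8 − ln(1 − lean)) / SD),

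and the chance of 3 or more responders follows from Binomial(6, p). For example, with SD 0.14 and a 5% lean, p = Φ((−0.2231 + 0.0513) / 0.14) = Φ(−1.23) = 0.110.

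| Assumed lean | p, SD 0.14 | p, SD 0.21 | p, SD 0.28 | P(≥3 of 6), SD 0.14 / 0.21 / 0.28 |
|---|---|---|---|---|
| 0 | 0.055 | 0.144 | 0.213 | 0.003 / 0.043 / 0.115 |
| 5% | 0.110 | 0.207 | 0.270 | 0.020 / 0.107 / 0.202 |
| 10% | 0.200 | 0.287 | 0.337 | 0.099 / 0.233 / 0.327 |

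**4. A different model.** Taking percent change as normal with SD 10, 15 or 20 points and no true change, P(≥3 of 6) is 0.0002, 0.012 and 0.055 without a lean. It is 0.055, 0.173 and 0.272 with a 10-point lean. The levels differ but the pattern is the same.

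**5. Free choice of window or lesion.** Under the same model with SD 15 points, suppose the most favourable of three candidate windows or lesions were always taken, with correlation 0.5 to 0.9 between candidates. By simulation, the per-patient chance of a false 20% fall rises from 0.09 to 0.14-0.20. With SD 10 points it rises from 0.023 to 0.038-0.058. This is the extreme of selective choice, not a forecast.

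**The case against.** The case on the other side is substantial, and it limits what can be claimed.

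- **A reader might infer that scan order is known to the analyst.** The documents do not say so; they are silent. Scans are made under separate protocol 2011-053, which is not available here and may contain reading rules. Section VII nevertheless describes the quantification itself and mentions no masking, so the supportable statement is that none is stated.
- **A reader might infer that every step behind the primary value is a judgement.** That goes too far. SUVmax is a hottest-pixel value, on which the drawn edge has little effect, and SUVmean uses a 50% isocontour. Non-tumor tissue does not enter the SUVmax change; it serves the secondary tumor-to-background comparison.
- **A reader might count visibility as part of the problem.** The plan says "We will also assess if the NET is visible above background at baseline". A secondary assessment made at baseline only cannot push the pre-to-post change toward the 20% cut.
- **A reader might infer that a lean could never be found later.** Section IX has the images kept, so a masked re-read would remain possible.
- **Lesion and window are not wholly free.** Eligibility requires a lesion judged suitable for AMT-PET from standard imaging, and the scan covers only the area containing the tumor. The window has a criterion, and finding it is a declared aim with a tracer that Section II says is untested in carcinoid tumors. This stands, but several lesions may share the field of view, and the criterion does not require the same window at both scans.
- **The sizes are assumed.** No document supports a lean of 5 or 10%. With no lean at all, the assumed SD range alone moves the false-responder rate from about 6% to 21%, and masking does not touch that noise.

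**Conclusion.** The point holds as a gap in specification. The frame window is set after the curves are examined and is not tied to both scans, no index lesion is defined, and masking to scan order is not stated. The part that rests on the plan's own figures is firm: one patient crossing the 20% cut moves the one-sided 90% lower limit from 0.093 to 0.201 and so decides the 0.2 goal.

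The size of any bias is not known. Under the assumed SDs, a lean of 5% would lift the per-patient false-responder rate to 11-27%, and a lean of 10% to 20-34%, from a starting range of about 6-21%. These figures show sensitivity; they are not evidence that a lean will occur. The sample size and the 0.201 lower limit do not change. The change should be made because it is cheap and less open to bias than looking first and choosing afterwards.

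**What to change.** Add to Section VII:

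1. Name one index lesion per patient from the eligibility imaging, and record it before any AMT quantification.
2. After both scans of a patient have been acquired, relabel them with codes, remove the dates and present them in random order.
3. Have the existing analyst apply one common frame window to both scans and record SUVmax and SUVmean.
4. Lock these values before the scan order is revealed.

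If protocol 2011-053 already contains equivalent reading rules, a cross-reference would do for those parts.

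The cost is relabelling 12 scans (6 patients × 2) and holding quantification until Scan 2. No extra reader, scan or patient procedure is needed. Patients go off study after Scan 2, and nothing in the plan depends on an earlier SUV result. Masking may be imperfect if a large drug effect gives the order away, but it would still help with the patients near the cut, who decide the count.

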Following registration, patients should begin protocol treatment within 7 days of baseline AMT PET imaging. Issues that would cause treatment delays should be discussed with the Principal Investigator, [name] at [contact]; [contact], or contact the study coordinators. If a patient does not receive protocol therapy following registration, the patient's registration on the study may be cancelled. The study coordinator should be notified of cancellations as soon as possible.

Registration Process

To register a patient, the following documents should be completed by the research nurse or data manager and faxed or emailed to the study coordinator:

- Copies of required laboratory tests, scans.
- Signed patient consent form.
- HIPAA authorization form.
- Eligibility checklist.
- Completed registration form.

To complete the registration process, the study coordinator will:

• Register the patient on the study

Off-Study Criteria

• Patients will be considered to have gone off of study following the completion of the second AMT-PET scan. They may elect to continue telotristat ethyl therapy under the supervision of their physician as part of standard treatment. Cost of continued standard treatment will be charged to the patient's insurance and patient.

V. TREATMENT PLAN

AMT-PET Imaging

- Scan 1: Baseline within 7 days prior to the start of telotristat ethyl treatment.
- Scan 2: On day 9-14 of telotristat ethyl administration.
- Patients cannot eat protein containing foods for 6 hours prior to the AMT-PET studies, to ensure stable plasma tryptophan and large neutral amino acid levels during the duration of the study. They can have water and soft drinks.
- The final dose of telotristat ethyl on day 9-14 should be taken within 6 hours of the scan and should be taken along with high fat foods, but no protein. This may include oils, olives, low protein breads with margarine. The choice of such foods will be discussed with the patient at the time of enrollment. Note that this dietary restriction only applies for scan 2 since patients need to take telotristat ethyl with fat.
- Blood (approximately 3 tsp) will be drawn to measure drug levels and tumor hormone levels (including serotonin) in the blood prior to each scan. These will be done by the hospital and company laboratories.

Agent Administration

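### A 20% SUVmax fall counts as response, but nothing in the plan shows whether it exceeds scan-to-scan variation or reflects a shift common to the whole scan

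*Combined protocol and SAP*

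**What the plan says.** The primary endpoint is a per-patient responder count: "The proportion of patients who achieved SUVmax reduction of 20% or more between baseline and followup will be the primary measurement" (Section VII, item 3). SUVmax is read from the hottest tumor pixel, with neighbouring planes (Section VII, item 1). Section VIII describes the design: "This is a single arm single institution prospective proof-of-concept study". The aim of the sizing is "to show the proportion of patients who achieved SUVs reduction is at least 0.2 or higher", and the calculation reads "A sample size of 6 produces a one-sided 90% lower-limit confidence interval at (0.201, 1) using Clopper-Pearson formula", "when the expected proportion is 0.5". For reporting, "The primary endpoint will be reported as proportions with two-sided exact 95% confidence limit". A paired t test on the before and after SUVs is also planned, if normality holds.

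Each patient has two scans (Section V). The first is "Scan 1: Baseline within 7 days prior to the start of telotristat ethyl treatment"; the second falls on treatment day 9 to 14. The scans can thus be about three weeks apart (7 + 14 = 21 days). A protein fast precedes both scans. Section V also has the last dose before scan 2 taken with high-fat, protein-free food, and says that this applies to scan 2 alone.

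On non-tumor tissue, Section VII states: "The AMT uptake in ROIs representing tumor and non-tumor tissue will be characterized in the following two ways". The one clear use of that measurement is the baseline contrast with tumor (Section I, secondary objective a). Section VII, item 3 also mentions a percent difference between tumor and background, without saying plainly whether this is at baseline only. No rule sets tumor change against non-tumor change. The documents give no repeatability figure and no rationale for the 20% cut or the 0.2 goal. Section II notes that the tracer has not been tried in carcinoid tumors.

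**The concern.** With no control arm and one scan on each side of treatment start, anything that lowers measured uptake at scan 2 is counted as response. Two kinds of non-drug change matter, and they behave differently.

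- **Random scan-to-scan noise** pushes some patients past the cut by chance.
- **A shift common to the whole scan**, for example from the different food conditions before scan 2, moves every patient in the same direction.

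The second is the more serious for a proof-of-concept claim. It raises the responder proportion and also enters the mean change that the paired t test examines, so the two analyses would agree with each other and could both be wrong. Non-tumor tissue from the same images could show such a shift, but the plan does not say that it will be used for this.

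**Working it through.** **Inputs from the documents:** n = 6; cut = 20% fall; goal = 0.2; expected proportion = 0.5; one-sided 90% Clopper-Pearson limit for sizing; two-sided exact 95% interval for reporting.

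**Assumptions (no figure in the documents):** log-normal measurement error, per-scan within-patient CV from 5% to 25%, no drug effect, and where stated a whole-scan fall *s* of 5% or 10%.

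**1. The plan's own figure.** For 3/6 the one-sided 90% lower limit is the 10% quantile of Beta(3, 4) = 0.2009, which reproduces 0.201. The implied rule of at least 3/6 has error P(X ≥ 3 | p = 0.2) = 9.9% and power 65.6% at p = 0.5. The two-sided 95% interval for 3/6 is 0.118 to 0.882; for 4/6 its lower limit is 0.223.

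**2. Random noise only.** The SD of the log ratio of two scans is sqrt(2 × ln(1 + CV²)). The no-effect responder rate is q = Φ(ln 0.8 / SD), with ln 0.8 = −0.223. The chance of 3 or more is 1 − (1−q)⁶ − 6q(1−q)⁵ − 15q²(1−q)⁴. At CV 15%, for example, SD = 0.211, −0.223/0.211 = −1.06 and q = 14.5%.

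| CV | No-effect responder rate | Chance of ≥3/6 |
|---|---|---|
| 5% | 0.1% | <0.1% |
| 10% | 5.7% | 0.3% |
| 15% | 14.5% | 4.3% |
| 19% | 20% | 10.0% |
| 25% | 26.1% | 18.7% |

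Up to a CV of about 19%, noise alone stays within the 10% error that the sizing already accepts.

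**3. Common shift, no drug effect.** q = Φ((ln 0.8 − ln(1 − s)) / SD). For s = 10% the numerator is −0.223 + 0.105 = −0.118.

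| Shift | CV | Responder rate | Chance of ≥3/6 |
|---|---|---|---|
| 5% | 10% | 11.2% | 2.1% |
| 5% | 15% | 20.8% | 10.8% |
| 10% | 10% | 20.2% | 10.1% |
| 10% | 15% | 28.8% | 23.4% |

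**4. Paired t test.** On the log scale with 6 pairs, 5 degrees of freedom and noncentrality √6 × 0.105/SD, a 10% shift without drug effect gives two-sided p < 0.05 in the direction of a fall about 32% of the time at CV 10% and 17% at CV 15%. The nominal figure in that direction is 2.5%.

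**5. What a tumor-to-reference ratio would do.** With tumor CV 15%, reference CV 10% and independent errors, SD = sqrt(2 ln 1.0225 + 2 ln 1.01) = 0.254. Then q = Φ(−0.223/0.254) = 19.0% and the chance of ≥3/6 is 8.7%. A shift that scales tumor and reference equally cancels, so these figures hold with or without it. Without the ratio they are 14.5% and 4.3% with no shift, and 28.8% and 23.4% with a 10% shift.

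**The case against.** The strongest reply is that the design already tolerates chance responders. The aim is a lower confidence limit of 0.2, not an observed 20%, and step 2 shows that this covers random noise up to a CV of about 19%. The reported two-sided 95% interval is stricter: its lower limit passes 0.2 only from 4/6. The no-effect chance of that is 15q⁴(1−q)² + 6q⁵(1−q) + q⁶, or 0.5% at CV 15%, and 6.2% with a 10% shift (q = 0.288). All of this stands. A reader might infer that responses cannot be told from noise at all, or that an inactive drug would deliver the target proportion. The documents do not support either reading: both depend on a CV that they do not give, and at 5% to 10% the noise problem is slight.

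A reader might also infer that nothing guards against differences in injected dose or plasma amino acids. That is not so. SUV is defined relative to injected dose and weight, and the protein fast is there to hold plasma tryptophan steady. SUVmean and, where the left ventricle is in view, kinetic modelling give further checks. These measures limit known sources of shift, but none shows what remains, and the food difference before scan 2 is part of the design. Nor do the documents exclude follow-up use of background; they leave it unclear.

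Finally, a normal-tissue region is an imperfect reference. It does not reproduce the single-pixel noise of a tumor, and the drug may act on it. A bare rule that tumor must fall more than reference, with no margin, would pass about half the time with no effect and symmetric errors. That stands too, and is why the reference should inform the interpretation and not become a success criterion.

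**Conclusion.** The point holds in a limited form. The plan gives no basis for judging whether a 20% SUVmax fall exceeds scan-to-scan variation or is part of a whole-scan shift, and no rule uses the non-tumor regions for that purpose. Random noise alone is a modest concern up to an assumed CV of about 19%. A common shift is the material one: at an assumed 10% fall, the chance of the 3/6 result on which the sizing rests goes from 0.3% to 10% at CV 10%, and from 4% to 23% at CV 15%, with no drug effect. Every CV and shift value here is an assumption. The documents show that conditions differ between scans, not that the difference changes uptake. This is a worthwhile improvement to a six-patient pilot; it does not invalidate the design.

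**What to change.** Keep the primary endpoint and add no new success gate. In Sections VII and VIII:

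- Prespecify one non-tumor reference region, with tissue, size and location stated, measured with the same statistic and time frames at both scans.
- Report its percent change, and the number of patients whose reference falls by 20% or more, beside the primary proportion.
- Repeat the responder analysis on the tumor-to-reference ratio as a sensitivity analysis.
- State that if the reference falls to a similar degree, the tumor fall will not be attributed to TPH inhibition.
- Give the source of the 20% cut and the 0.2 goal, or say that there is none. The reference region cannot fill that gap.

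**Cost:** a few sentences and one more region per scan, on images already acquired. The ratio adds the reference's own noise: in the example above the no-effect responder rate rises from 14.5% to 19.0%. The reference detects common shifts but not tumor single-pixel noise. A tissue with TPH activity would understate the drug effect, so the choice should be made and justified in advance.

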The measurement of the uptake and retention of AMT will be quantitated by maximum standardized uptake values (SUVmax) and compartmental modeling (in tumors with the left ventricle of the heart in the field-of-view) before and after treatment with telotristat ethyl. The proportion of patients whose reduction in AMT uptake between baseline and follow-up is \geq 20% will be the primary endpoint. We will also assess if the NET is visible above background at baseline and will also quantify the percent difference in AMT uptake between the tumor mass and background. Using time-activity curves, we will also identify the optimal time frame where tumoral AMT uptake peaks.

STATISTICAL PLAN:

This is a single arm single institution prospective proof-of-concept study. The proportion of patients, who achieved SUVmax reduction of 20% or more, will be estimated and exact (Clopper-Pearson) confidence interval will be calculated. Paired t test will be used for pre- and post- treatment SUVs if normality assumption holds. The relationship of one PET parameter to another will be visualized with scatter plot and measured using linear regression models.

I. OBJECTIVES

- Primary Objective: The primary objective of this pilot study is to evaluate the effect of telotristat ethyl treatment in patients with advanced neuroendocrine tumors (NETs) using α-[¹¹C]methyl-L-tryptophan (AMT)-positron emission tomography (PET) as measured by changes in tumor maximum standardized uptake value (SUVmax).
- 2. Secondary Objectives:
 - **a.** Show that NETs will have increased AMT uptake on PET, as compared to surrounding nontumor tissue at baseline
 - **b.** Use compartmental modeling (in tumors with the left ventricle of the heart in the field-of-view) to measure change in AMT retention.
 - c. Measure change in AMT retention as SUVmean

II. BACKGROUND

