Telotristat ethyl is an oral small-molecule TPH inhibitor that has a high molecular weight and acidic moieties, which inhibit it from crossing the blood-brain barrier (Liu et al., 2008; Lapuerta et al., 2015). As the drug has recently become available for clinical treatment of carcinoid-related diarrhea, there is an urgent need to evaluate non-invasive techniques to assess drug effects.

Telotristat ethyl has been shown to inhibit tumor growth in a retrospective study of 200 patients with NET (Morse et al., 2020). After initiation of telotristat ethyl they observed a mean decrease of 0.6 cm in tumor size (p = 0.006) and decrease in tumor growth (p = 0.045). It will be of interest to determine using AMT-PET if we can measure inhibition of serotonin synthesis and serve as a biomarker in studies assess this activity of this pathway. The use of telotristat ethyl may inhibit tumor proliferation and the image of AMT uptake may provide a predictive marker of this effect. If promising, PET imaging with AMT or an ¹⁸F-labeled analog (with a longer half-life) (see, e.g., Michelhaugh et al., 2016; Giglio et al., 2017) could be useful to monitor effectiveness of TPH inhibition in future multicenter studies and clinical trials.

The central hypothesis of this pilot study is that (i) that telotristat ethyl (Xermelo[™]) (Kulke et al., 2017), a recently FDA-approved TPH inhibitor drug, will decrease tumoral AMT uptake and trapping as compared to values measured at baseline before the start of treatment. (ii) carcinoid tumors will show increased AMT uptake on PET, as compared to surrounding non-tumor tissue at baseline.

As a first step, in this pilot study we will perform AMT-PET imaging in 6 evaluable patients with previously diagnosed mNETs, not previously treated with TPH inhibitor, to characterize the baseline and post-treatment uptake patterns of these tumors and test the feasibility to use AMT-PET for evaluating activity of TPH after inhibitor treatment.

III. PATIENT SELECTION

Inclusion:

- 1. Eligible patients must be \geq 18 years of age.
- 2. Histopathologically confirmed, well-differentiated metastatic NETs
- 3. Receiving stable-dose somatostatin analog (long-acting release [LAR], depot) for > 3 months before enrollment.
- 4. Patients with 5-HIAA levels above or below the upper limit of normal range and those with unknown values at baseline are allowed to participate.
- 5. Able to lie within the PET scanner for at least 70 minutes while undergoing scanning.

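### N=6 is justified by a one-sided 90% exact limit (0.201 at 3/6), but the plan commits to reporting a two-sided 95% interval, whose lower limit at 3/6 is 0.118, below the 0.2 goal

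*Combined protocol and SAP*

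**What the plan says.** All the relevant text is current, and most of it is in one paragraph of Section VIII (Statistical Plan).

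- **Goal.** Under Power calculation, alongside feasibility, the aim is "to show the proportion of patients who achieved SUVs reduction is at least 0.2 or higher". This 0.2 is a proportion of patients. It is separate from the 20% SUV reduction that defines a responder.
- **Sizing criterion.** The next sentence derives the criterion from that goal: "Hence, we will calculate the minimum sample size to achieve a confidence lower limit no less than 0.2".
- **Basis for N.** Six patients are said to give a "one-sided 90% lower-limit confidence interval at (0.201, 1) using Clopper-Pearson formula when the expected proportion is 0.5". Section II (Background) gives the same number: "in this pilot study we will perform AMT-PET imaging in 6 evaluable patients".
- **Reporting.** Earlier in Section VIII: "The primary endpoint will be reported as proportions with two-sided exact 95% confidence limit".
- **Protocol Summary, Statistical Plan.** The proportion "will be estimated and exact (Clopper-Pearson) confidence interval will be calculated", with neither level nor sidedness given.

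No section says that the one-sided 90% limit will be reported or used to judge the goal, and none explains why two levels appear.

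**The concern.** The sizing text allows 0.10 in the lower tail; the reporting text allows 0.025. An N chosen to bring one limit just over 0.2 need not bring the other there. If it does not, a result equal to the planning assumption would count as reaching 0.2 under the sizing text, while the published interval would include values below 0.2. The limit on which N rests would not appear among the planned results. Because the plan does not say which limit answers its goal, that choice could be made after the number of responders is known.

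**Working it through.** **Inputs.** n = 6 evaluable patients (Sections II and VIII). Expected proportion 0.5, that is x = 3. Goal 0.2. Sizing limit one-sided 90% (a = 0.10 in the lower tail). Reported interval two-sided exact 95% (a = 0.025 in each tail). Clopper-Pearson method. All are from Section VIII unless noted.

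**Formula.** The Clopper-Pearson lower limit L solves P(X ≥ x | n, L) = a. Equivalently, L is the a-quantile of a Beta(x, n − x + 1) distribution.

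**Step 1: the plan's own figure.** With x = 3, n = 6 and a = 0.10, L = 0.2009, which rounds to the stated 0.201. Check: P(X ≥ 3 | 6, 0.2009) = 0.1000. The figure reproduces. With half the patients responding, 2/4 gives 0.143 and 3/6 gives 0.201, so 6 is the smallest even n that meets the criterion under this limit.

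**Step 2: the interval to be reported.** With x = 3, n = 6 and a = 0.025, L = 0.1181. Check: P(X ≥ 3 | 6, 0.1181) = 0.0250. The upper limit is 0.8819, so the interval is 0.118 to 0.882.

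**Step 3: a hand check at 0.2.** A lower limit reaches 0.2 exactly when the upper-tail probability at p = 0.2 is no larger than a.

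- P(X ≥ 3 | 6, 0.2) = 1 − (0.2621 + 0.3932 + 0.2458) = 0.0989. This is below 0.10 but above 0.025, so 3/6 passes on the sizing limit and fails on the reported one.
- P(X ≥ 4 | 6, 0.2) = 0.0154 + 0.0015 + 0.0001 = 0.0170. This is below 0.025, so 4/6 passes on both.

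**Step 4: all outcomes.**

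| Responders | One-sided 90% lower limit | Two-sided 95% lower limit | Agree on 0.2? |
|---|---|---|---|
| 0/6 | 0 | 0 | yes (both below) |
| 1/6 | 0.017 | 0.004 | yes (both below) |
| 2/6 | 0.093 | 0.043 | yes (both below) |
| **3/6** | **0.201** | **0.118** | **no** |
| 4/6 | 0.333 | 0.223 | yes (both above) |
| 5/6 | 0.490 | 0.359 | yes (both above) |
| 6/6 | 0.681 | 0.541 | yes (both above) |

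**Step 5: how often it matters** (binomial, n = 6).

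| True proportion | P(X = 3) | P(X ≥ 3), sizing limit reaches 0.2 | P(X ≥ 4), reported limit reaches 0.2 |
|---|---|---|---|
| 0.2 | 0.0989 − 0.0170 = 0.082 | 0.099 | 0.017 |
| 0.5 | 20/64 = 0.313 | 42/64 = 0.656 | 22/64 = 0.344 |
| 0.6 | 0.277 | 0.821 | 0.8208 − 0.2765 = 0.544 |
| 0.7 | 0.185 | 0.930 | 0.9295 − 0.1852 = 0.744 |

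**Step 6: N under the reported interval.** With half the patients responding, the two-sided 95% lower limit is 0.118 at 3/6, 0.157 at 4/8, 0.187 at 5/10 and 0.211 at 6/12. The stated criterion would first be met at an even n of 12. This shows only that six patients satisfy the criterion through the one-sided 90% limit and not through the interval to be reported.

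**The case against.** The best defence is that the two statements do different jobs. One explains how N was chosen and the other how the result will be presented. Both can be followed at once, neither is miscalculated, and sizing on a one-sided limit while reporting a two-sided interval is not in itself a contradiction. The plan has no hypothesis test, success threshold or go/no-go step, and its goal also includes feasibility. The Protocol Summary gives no level for its exact interval, so it does not rule out the one-sided limit. With the count reported, any reader can compute the 90% limit. Finally, the mismatch is conservative: it understates a 3/6 result.

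Much of this stands. The plan contains no arithmetic error, no action depends on the result, and one outcome of seven is affected. It is also an inference that 3/6 would be called a success, since the sizing text is a planning calculation.

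The mismatch remains, however. Section VIII states an aim to show at least 0.2 and derives its sample size criterion directly from that aim; this is the only quantitative basis for N. Different limits for sizing and reporting are acceptable when the plan says which one answers its goal, and this one does not. The only reporting interval with a stated level is the one that fails at the planning value. That a reader could compute the other limit does not settle in advance which limit counts.

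**Conclusion.** The concern holds. Six patients deliver the stated property, a lower limit of at least 0.2 at the expected proportion, only through a limit that the analysis text does not mention. Under the interval it does commit to, the same result gives 0.118. The disagreement is confined to 3/6, whose probability is 31% at a true proportion of 0.5, 28% at 0.6 and 19% at 0.7. At 0.5, the choice of limit changes the chance of reaching 0.2 from 66% to 34%.

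These figures assume exactly six evaluable patients, independent binary outcomes, and Clopper-Pearson limits for both intervals, as the plan specifies. The point should be fixed because it concerns the primary endpoint and costs almost nothing, but its consequence in a pilot of this size is small. It does not show that 0.201 is wrong or that N must change.

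**What to change.** Add to the analysis text of Section VIII, and align the Protocol Summary with it:

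> The goal of a proportion of at least 0.2 will be judged by the one-sided 90% Clopper-Pearson lower limit; with 6 evaluable patients it is met with at least 3 responders. This limit will be reported. The two-sided 95% exact interval is descriptive.

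Optionally, state the operating characteristics of this rule: the chance of meeting the goal is 9.9% at a true proportion of 0.2, and 66%, 82% and 93% at 0.5, 0.6 and 0.7.

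The cost is two or three sentences. N, the endpoint, the method and the reported 95% interval all stay as they are.

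If the sponsor would rather judge the goal by the two-sided 95% limit, the plan should say so and state that at least 4 of 6 responders are then needed. The present justification of N=6 would no longer apply. It would have to be replaced, or the study planned at about 12 patients; the 6 extra patients mean about one more year at the stated accrual of 6 per year. The first option avoids this and fits the sizing text as it stands.
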